9.3. Efficacy Analyses

9.3.1. Primary Endpoint Analyses

The primary efficacy endpoint is the sustained castration rate, defined as the cumulative probability of testosterone suppression to ≤ 50 ng/dL (1.7 nmol/L) while on study treatment from Week 5 Day 1 (Study Day 29) through Week 49 (Study Day 337). This probability will be estimated for each treatment group using the Kaplan-Meier method with the confidence interval calculated using the exponential Greenwood formula via log-log transformation of the survival function. Patients who discontinue treatment prior to observing a testosterone level > 50 ng/dL (1.7 nmol/L) will be censored at the last testosterone assessment prior to discontinuation. Detailed censoring rules will be described in the statistical analysis plan.

There are 2 separate evaluation criteria for the primary efficacy endpoint to support different regulatory requirements for assessing benefit:

- Evaluation Criterion 1: to determine whether the sustained castration rate for relugolix is greater than or equal to 90%. The lower bound of the 95% confidence interval for the cumulative probability of sustained testosterone suppression in the relugolix treatment group will be calculated and must be greater than or equal to 90% to meet this criterion.
- Evaluation Criterion 2: to establish the non-inferiority of relugolix compared to leuprolide acetate 3-M depot as assessed by the cumulative probability of sustained testosterone suppression. The lower bound of the 95% confidence interval for the difference in the cumulative probability of sustained testosterone suppression between the 2 treatment groups will be calculated and must be greater than or equal to the non-inferiority margin of -10% to meet this criterion. The confidence interval of the treatment difference will be calculated using the formula $\hat{V}[\hat{S}_1(t) - \hat{S}_2(t)] = \hat{V}[\hat{S}_1(t)] + \hat{V}[\hat{S}_2(t)]$, where each of the variance of the Kaplan-Meier estimate will be calculated using the Greenwood's formula $\hat{V}[\hat{S}(t)] = \hat{S}(t)^2 \left[\sum_{j:t_{(j)} \leq t} \frac{d_j}{n_j(n_j - d_j)} \right]$; n_j denote the number of patients at risk at time $t_{(j)}$ and d_j denote the number of events observed at time $t_{(j)}$ [Lachin, 2000].

The evaluation criteria used for the primary efficacy endpoint assessment will be determined by regional regulatory requirements and will be prespecified in separate regional statistical analysis plans. The 2-sided type I error rates for the final analyses will be controlled at 0.05 separately for each regional analysis.

9.3.2. Secondary Endpoint Analyses

If the result of the primary endpoint is statistically significant, the secondary endpoints will be analyzed. The methods and procedures necessary to maintain a study-wide 2-sided type I error rate of 0.05 across primary and secondary endpoint testing will be described in the statistical analysis plan.

- Castration rate defined as the cumulative probability of testosterone suppression to ≤ 50 ng/dL (1.7 nmol/L) prior to dosing at Week 1 Day 4, and prior to dosing at Week 3 Day 1 will be summarized by treatment group using the Kaplan-Meier method;
- Profound castration rate defined as the cumulative probability of testosterone suppression of ≤ 20 ng/dL (0.7 nmol/L) while on treatment from Week 25 Day 1 through Week 49 Day 1 will be estimated for each treatment group using the Kaplan-Meier method. The difference in the cumulative probabilities between the relugolix group and the leuprolide acetate group will be provided, along with the 95% confidence interval calculated in the same manner as in the primary analysis of the primary endpoint;
- PSA response and percent change from baseline in PSA at Week 3 and Week 5 will be summarized and compared between the relugolix group and the leuprolide acetate group;
- Proportions of patients who have a PSA concentration < 0.2 ng/mL (0.2 μ g/L) at Week 25 will be summarized by treatment group. The proportions will be compared between the relugolix group and the leuprolide acetate group by constructing a 95% confidence interval for the difference in proportions;
- Time to testosterone recovery in approximately 100 patients randomized to relugolix and approximately 50 patients randomized to leuprolide acetate who complete 48 weeks of treatment and who do not start alternative androgen deprivation therapy within the following 12 weeks (or within 24 weeks following the last received leuprolide acetate 3-M depot injection) will be compared between the relugolix group and the leuprolide acetate group;
- Absolute values and changes from baseline in the scores of the EORTC-QLQ-C30 global health domain and the EORTC-QLQ-PR25 sexual activity and hormonal-treatment-related symptom subdomains will be summarized by treatment group. The least square means at Week 49 will be compared between the relugolix group and the leuprolide acetate group by constructing a 95% confidence interval for the difference in the least square means using a mixed model for repeated measures;
- Absolute values and changes from baseline of the remaining domains in the EORTC QLQ-C30 and EORTC QLQ-PR25, as well as EQ-5D-5L will be summarized by treatment group. The least square means at Week 49 will be compared between the relugolix group and the leuprolide acetate group by constructing a 95% confidence interval for the difference in the least square means using a mixed model for repeated measures; and
- Time to PSA progression;
- Proportion of patients with confirmed PSA progression among those who have achieved sustained testosterone suppression during the 48-week treatment.

Further details of the secondary analyses will be described in the statistical analysis plan.

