- Evaluation Criterion 2: to establish the non-inferiority of relugolix compared to leuprolide acetate 3-M depot as assessed by the cumulative probability of sustained testosterone suppression to castrate levels. The lower bound of the 95% confidence interval for the difference in the cumulative probability of sustained testosterone suppression to castrate levels between the 2 treatment groups will be calculated and must be greater than or equal to the non-inferiority margin of -10% to meet this criterion.

The 2-sided type I error rate will be 0.05 for each individual evaluation criterion.

Secondary Efficacy Endpoints:

1. Castration rate: the cumulative probability of testosterone suppression to ≤ 50 ng/dL (1.7 nmol/L) prior to dosing on Week 1 Day 4, and prior to dosing on Week 3 Day 1;
2. Profound castration rate: the cumulative probability of testosterone suppression to ≤ 20 ng/dL (0.7 nmol/L) from Week 25 through Week 49;
3. PSA response rate: proportion of patients with a $\geq 50\%$ decrease in PSA from baseline at Week 3 and confirmed at Week 5;
4. Undetectable PSA rate: proportion of patients with PSA concentration < 0.2 ng/mL (0.2 μ g/L) at the Week 25 visit;
5. Time to testosterone recovery in approximately 100 relugolix-treated and approximately 50 leuprolide acetate-treated patients who complete 48 weeks of treatment and do not start alternative androgen deprivation therapy within 12 weeks after the last dose of relugolix or within 24 weeks following the last received injection of leuprolide acetate. Kaplan-Meier methods will be used to describe survival distributions;
6. Quality of Life: absolute values and changes from baseline in the scores of the EORTC-QLQ-C30 global health domain, and the EORTC-QLQ-PR25 sexual activity and hormonal-

treatment-related symptom subdomains, at regular intervals during treatment, and as applicable at the Follow-up and/or End-of-Study visits will be presented. Additionally, absolute values and changes from baseline of the remaining domains in the EORTC QLQ-C30 and EORTC QLQ-PR25, as well as EQ-5D-5L, at regular intervals during treatment, and as applicable during the Follow-up visits will be presented. Change from baseline will be analyzed using mixed-model repeated measures methodology;

7. Time to PSA progression;
8. Proportion of patients with confirmed PSA progression among those who have achieved sustained testosterone suppression during the 48-week treatment period.

Exploratory Endpoints:

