4.3.1. Inclusion Criteria

A patient will be eligible for inclusion in this study only if all of the following inclusion criteria are met prior to randomization, unless otherwise specified:

1. Has voluntarily signed and dated the informed consent form prior to initiation of any screening or study-specific procedures;
2. Is a male aged 18 years or older on the day of signing and dating the informed consent form;
3. Has histologically or cytologically confirmed diagnosis of adenocarcinoma of the prostate;
4. Is a candidate for, in the opinion of the investigator, at least 1 year of continuous androgen deprivation therapy for the management of androgen-sensitive advanced prostate cancer with one of the following clinical disease state presentations:
 - a. Evidence of biochemical (PSA) or clinical relapse following local primary intervention with curative intent, such as surgery, radiation therapy, cryotherapy, or high-frequency ultrasound and not a candidate for salvage treatment by surgery; or
 - b. Newly diagnosed androgen-sensitive metastatic disease; or
 - c. Advanced localized disease unlikely to be cured by local primary intervention with either surgery or radiation with curative intent;

Note: radiotherapy, cryotherapy, or high frequency ultrasound are allowed after 2 months of androgen deprivation therapy.

5. Has a serum testosterone at the Screening visit of ≥ 150 ng/dL (1.50 ng/mL or 5.2 nmol/L);
6. Has a serum PSA concentration at the Screening visit of > 2.0 ng/mL (2.0 μ g/L), or, when applicable, post radical prostatectomy of > 0.2 ng/mL (0.2 μ g/L) or post radiotherapy, cryotherapy, or high frequency ultrasound > 2.0 ng/mL (2.0 μ g/L) above the post interventional nadir;
7. Has an Eastern Cooperative Oncology Group (ECOG) performance status of 0 or 1 at initial screening and at baseline (refer to [Appendix 1](#));
8. Is a male patient who, even if surgically sterilized (ie, status post vasectomy):
 - a. Agrees to use a male condom if having sex with a woman of childbearing potential or a pregnant woman, during the entire study Treatment Period and through 4 months after the last dose of study drug; or
 - b. Agrees to practice true abstinence, when this is in line with the preferred and usual lifestyle of the patient. Periodic abstinence (eg, calendar, ovulation, symptothermal, postovulation methods for the female partner) and withdrawal are not acceptable methods of contraception;

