9.1. Randomization Methods

Central randomization will be used and treatment allocation will be 2:1, relugolix to leuprolide acetate 3-M depot. Randomization will be stratified by the following factors:

- Geographic Region: North and South America versus Europe versus Asia and Rest of World;
- Presence of Metastatic Disease: yes versus no;
- Baseline Age: ≤ 75 years old versus > 75 years old.

Stratified efficacy analyses will incorporate these 3 stratification factors unless otherwise specified.

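### Week 25 undetectable-PSA rate: the stated comparison ignores baseline PSA, which leaves it valid but less precise than it need be

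*Protocol*

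**What the plan says.** Inclusion criterion 6 (Section 4.3.1) sets two kinds of entry floor for PSA. The general rule is "Has a serum PSA concentration at the Screening visit of > 2.0 ng/mL". For men who have had surgery it is, "when applicable, post radical prostatectomy of > 0.2 ng/mL". Men treated with radiotherapy, cryotherapy or ultrasound must be more than 2.0 ng/mL above their nadir. There is no upper limit.

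The synopsis lists among the secondary endpoints the "Undetectable PSA rate: proportion of patients with PSA concentration < 0.2 ng/mL" at Week 25. Section 9.3.2 summarises this by arm ("Proportions of patients who have a PSA concentration < 0.2 ng/mL") and compares the arms "by constructing a 95% confidence interval for the difference in proportions".

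Section 9.1 says: "Stratified efficacy analyses will incorporate these 3 stratification factors unless otherwise specified". The three are region, metastatic disease and age. Section 9.3.2 closes with: "Further details of the secondary analyses will be described in the statistical analysis plan".

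**The concern.** The responder threshold is the same number as the entry floor for post-prostatectomy men, one tenth of the general entry floor, and far below the PSA that some men with newly diagnosed metastatic disease may bring. One label, undetectable, therefore covers very different hurdles. Men near the floor will tend to respond on either drug, and men with very high PSA will seldom respond on either.

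If response varies this much with a baseline value, a comparison that leaves that value out carries avoidable variance. What is at stake is the width of the confidence interval on a secondary endpoint, and how easily a reader can tell what the overall rate represents.

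**Working it through.** **The plan's own figure.** The protocol gives no expected rate and no power for this endpoint, so there is nothing to reproduce. The sample-size figures in Section 9.9 concern testosterone suppression and have no bearing here.

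**Required fall.** To get below 0.2 ng/mL from baseline *b*, PSA must fall by more than 1 − 0.2/*b*:

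| Baseline (ng/mL) | Required fall |
|---|---|
| 0.21 | 1 − 0.2/0.21 = 4.8% |
| 0.5 | 60% |
| 1 | 80% |
| 2.1 | 1 − 0.2/2.1 = 90.5% |
| 10 | 98% |
| 200 | 1 − 0.2/200 = 99.9% |

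This step needs no assumption about the population.

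**Why adjustment helps: a two-group illustration.** Suppose a share *s* of men respond at 90% and the rest at 20% (assumed values). The crude variance is proportional to p(1 − p), with p = 0.9*s* + 0.2(1 − *s*). The stratified variance is proportional to 0.09*s* + 0.16(1 − *s*).

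| *s* | p | Crude p(1 − p) | Within strata | Ratio | Interval narrower by |
|---|---|---|---|---|---|
| 0.1 | 0.27 | 0.197 | 0.153 | 0.78 | 1 − √0.78 = 12% |
| 0.3 | 0.41 | 0.242 | 0.139 | 0.57 | 24% |
| 0.5 | 0.55 | 0.248 | 0.125 | 0.51 | 29% |

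**Simulation of the trial.** There were 610 and 305 men. The assumptions were: log-normal baseline PSA above each entry floor, with medians about 1.2 ng/mL (post-prostatectomy) and 17 ng/mL (others); a mean log fall of 3.5 with SD 1.2; and a treatment effect of 0 or 0.3 on the log scale. The stratified estimate used baseline-PSA quintiles, weighted by size.

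| Post-prostatectomy share | Effect | Mean difference, crude / stratified (points) | SD, crude / stratified (points) | Variance ratio |
|---|---|---|---|---|
| 10% | 0 | 0.1 / 0.1 | 3.27 / 2.62 | 0.64 |
| 10% | 0.3 | 6.1 / 6.1 | 3.32 / 2.68 | 0.65 |
| 30% | 0 | 0.1 / 0.1 | 3.49 / 2.53 | 0.53 |
| 30% | 0.3 | 5.6 / 5.6 | 3.50 / 2.57 | 0.54 |
| 50% | 0 | −0.1 / −0.1 | 3.51 / 2.56 | 0.53 |
| 50% | 0.3 | 5.1 / 5.1 | 3.47 / 2.37 | 0.47 |

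With no treatment effect, the crude comparison was significant in 4.6% to 5.3% of simulated trials, close to the nominal 5%. The crude SD agrees with the textbook formula: at a 44.7% response rate, √[0.447 × 0.553 × (1/610 + 1/305)] = 3.49 points. In the 30% null row, the 95% half-width falls from 1.96 × 3.49 = 6.8 points to 1.96 × 2.53 = 5.0 points.

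**Sensitivity to the assumptions.** A second set of inputs took 20% to 40% post-prostatectomy men with median PSA 1.5, others with median 15, a median Week 25 PSA of 2% of baseline, and log-SD 1.2 to 1.8. It gave ratios of 0.54 to 0.73. Response ran from 0.87–0.98 in the lowest baseline quintile to 0.06–0.17 in the highest. A third set gave 0.56 to 0.80. A ratio of 0.55 means an interval 1 − √0.55 = 26% narrower, and 0.80 means about 10% narrower. The 50% row above goes a little further, so roughly 0.55 to 0.80 is a working range, not a bound.

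**The case against.** The strongest objection is that Section 9.3.2 leaves further detail to the statistical analysis plan, and covariate adjustment of a secondary proportion is the sort of detail a protocol leaves there. A stratified difference is still a difference in proportions with a confidence interval, so the present wording does not forbid it. Section 9.1 also leaves room for other factors, and stratifying by metastatic disease, if it were applied here, would capture part of the gain. All of this stands. The most that can be said is that the protocol names no baseline-PSA adjustment, not that none is planned.

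It can also be said that the endpoint is meant to be absolute, and that change relative to baseline is covered by the confirmed 50% response and the percent change at Weeks 3 and 5. That is fair, and the endpoint should stay as it is. But those analyses do not sharpen the Week 25 comparison.

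Three stronger readings are tempting, and the documents support none of them:

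- **The endpoint mostly reflects where men started.** The documents give no baseline PSA distribution, post-prostatectomy share or expected rate, so this cannot be shown. It also confuses the rate within an arm with the difference between arms.
- **Chance imbalance in PSA biases the comparison.** Randomisation balances PSA in expectation, and the crude interval already allows for chance imbalance. The simulation shows nominal error and the same average estimate either way.
- **Men already below 0.2 ng/mL on Day 1 are counted as successes.** Entry requires more than 0.2 at Screening. PSA is drawn again at Baseline Day 1, so a man just above the floor could cross it untreated, but nothing shows that such men exist, still less in number.

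**Conclusion.** The point holds as a minor, optional improvement in precision. Response at Week 25 depends strongly on baseline PSA; that follows from the threshold and the entry criteria. The comparison as stated is valid and unbiased, with type I error near 5%. It is less precise than data already collected would allow: the variance under stratification is roughly 55% to 80% of the crude value, an interval about 10% to 26% narrower. The size rests wholly on assumed PSA distributions and falls, and is measured against a fully crude analysis. The conclusion on the primary endpoint is not touched.

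**What to change.** In Section 9.3.2, state that the Week 25 difference is a Mantel-Haenszel or standardised difference in proportions, stratified by Baseline Day 1 PSA category with post-prostatectomy men as a separate stratum, and report the crude difference alongside. Fix the cut points before database lock. With 2:1 allocation in each stratum, the Mantel-Haenszel weight is (2n/3)(n/3)/n = 2n/9, proportional to stratum size, so both forms aim at the same quantity as the crude difference.

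Keep all intent-to-treat patients. Any man below 0.2 ng/mL on Day 1 belongs in the lowest PSA stratum. Leaving such men out of the main analysis would depart from the population in Section 9.2, so exclusion should be a sensitivity analysis only.

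The cost is wording in the protocol and the analysis plan. The Schedule of Activities already collects Day 1 PSA and prostate cancer history for every man. If the analysis plan already contains such an adjustment, a cross-reference is enough.

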 - Profound castration rate defined as the cumulative probability of testosterone suppression to ≤ 20 ng/dL (0.7 nmol/L) while on study treatment from Week 25 Day 1 through Week 49 Day 1;
 - Time to testosterone recovery in approximately 100 patients randomized to relugolix and approximately 50 patients randomized to leuprolide acetate who complete 48 weeks of treatment and who do not plan to start alternative androgen deprivation therapy within the following 12 weeks (or within 24 weeks following the last injection of leuprolide acetate 3-M depot);
- Describe effects on PSA:
 - Proportion of patients with confirmed PSA response by Prostate Cancer Clinical Trials Working Group 3 guidelines at the Week 3 and Week 5 visits [[Scher, 2016](#)];
 - Proportion of patients with PSA concentration < 0.2 ng/mL (0.2 μ g/L) at the Week 25 visit;
- Absolute values and changes from baseline in the scores of the EORTC-QLQ-C30 global health domain, and the EORTC-QLQ-PR25 sexual activity and hormonal-treatment-related symptom subdomains, at regular intervals during treatment, and as applicable during the Follow-up and/or at End of Treatment visits;
- Absolute values and changes from baseline of the remaining domains in the EORTC QLQ-C30 and EORTC QLQ-PR25, as well as the EuroQol EQ-5D-5L questionnaire, at regular intervals during treatment, and as applicable during the Follow-up visits;
- Incidence of adverse events;
- Incidence of abnormalities in clinical laboratory data;
- Endocrine marker effects of relugolix and leuprolide acetate as measured as absolute value and change from baseline for:
 - LH at the Day 4, Week 5, Week 25, and Week 49 visits;
 - FSH at the Day 4, Week 5, Week 25, and Week 49 visits;
 - Dihydrotestosterone at the Week 5, Week 25, and Week 49 visits; and
 - Sex hormone binding globulin at the Week 5, Week 25, and Week 49 visits;
- Predose relugolix plasma concentrations;

- Single and repeat-dose plasma relugolix PK parameters such as maximum plasma concentration (C_{max}), area under the concentration-time curve from time 0 to the end of the dosing interval ($AUC_{0-\tau}$), and time to maximum plasma concentration (t_{max}) in a subset of patients from China (if enrolled) and Japan during the Day 1 visit.
- Time-to PSA progression;
- Proportion of patients with confirmed PSA progression among those who have achieved sustained testosterone suppression during the 48-week treatment.

Exploratory Endpoints

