4.7. Removal of Patients from Therapy

Patients may withdraw consent to participate in the study and discontinue treatment at any time for any reason. Investigators or the medical monitor may remove patients from therapy under this protocol for reasons of safety and/or lack of compliance as discussed below. Patients removed from therapy for any reason will undergo the assessments for the Week 49 visit on the Schedule of Activities. The End of Treatment is defined as the last dose of relugolix or 12 weeks after the last leuprolide acetate injection.

Follow-up visits to assess safety will be performed in all study patients. If the patient plans to start alternative androgen deprivation therapy less than 30 days after the End of Treatment visit, the Safety Follow-up visit may occur earlier, before the start of the alternative androgen deprivation therapy. Testosterone recovery will be evaluated in approximately 100 patients randomized to relugolix and approximately 50 patients to leuprolide acetate who complete 48 weeks of study drug treatment and, in the opinion of the investigator, are candidates for intermittent androgen deprivation therapy and will not be offered alternative androgen deprivation therapy upon completion of study therapy. These patients will return for the 60- and 90-day follow-up Testosterone Recovery visits.

The safety and/or compliance events shown in [Table 4-1](#) will result in the removal of patients from therapy either permanently or until the etiology of the problem has been identified and resolved.

Table 4-1 Removal of Patients from Treatment

Reason	Comment
Adverse event or intercurrent illness	Any intolerable adverse event to the patient that cannot be ameliorated by the use of adequate medical intervention, or that in the opinion of the investigator or medical monitor would lead to undue risk to the patient if dosing continued
Failed to meet eligibility criteria post randomization	If it is discovered after randomization that a patient failed to meet protocol entry criteria and continued participation poses an unacceptable risk to the patient's health
Dose hold	Relugolix dose hold that exceeds 10 consecutive days

Reason	Comment

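### Testosterone recovery: the analysis text selects men by whether they later restart androgen deprivation, contradicts the endpoint definition, and can bias the arm comparison

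*Protocol*

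**What the plan says.** References are to the later protocol version in the file, planned for about 915 patients.

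**Analysis text.** Section 9.3.2 takes about 100 relugolix and 50 leuprolide men who complete 48 weeks and "who do not start alternative androgen deprivation therapy within the following 12 weeks". For the leuprolide arm the window is given as "within 24 weeks following the last received leuprolide acetate 3-M depot injection". The section then says that time to recovery "will be compared between the relugolix group and the leuprolide acetate group". The synopsis statistical methods likewise keep men who "do not start alternative androgen deprivation therapy within 12 weeks after the last dose of relugolix" (with the matching leuprolide window) and add that "Kaplan-Meier methods will be used to describe survival distributions".

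**Endpoint text.** The synopsis list of secondary endpoints and the section 3 table describe men "who do not plan to start alternative androgen deprivation therapy within the following 12 weeks".

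**Entry to recovery follow-up.** Section 4.7 takes men who, in the investigator's opinion, "are candidates for intermittent androgen deprivation therapy and will not be offered alternative androgen deprivation therapy upon completion of study therapy". Section 6.4 and footnote c of Table 1-1 also rest on the investigator's view of the patient. Both add that men who have restarted do not attend the 60- and 90-day visits.

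Section 9.3.2 leaves further detail of the secondary analyses to the SAP, but the protocol itself sets the analysis population.

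**The concern.** Planning not to restart is known at the end of treatment. Not having restarted is known only once the outcome window has almost closed. A set defined the second way conditions on behaviour during follow-up, and that behaviour may depend on the outcome: testosterone and PSA are measured at the follow-up visits, the trial is open-label, and restarting is a clinical decision.

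Kaplan-Meier estimation exists to use partial follow-up, whereas the literal rule discards it. If restart is linked to recovery, each curve is biased. If recovery speed or restart behaviour also differs between arms, the biases need not cancel in the difference. At stake is the between-arm statement on how quickly testosterone returns.

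**Working it through.** The plan gives no power, event count or effect size for this endpoint, so there is no figure to reproduce.

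**1. Timing.** The last leuprolide injection is at Week 37, and 37 + 24 = Week 61. Relugolix ends at Week 49, and 49 + 12 = Week 61. The windows therefore match across arms. Twelve weeks is 12 × 7 = 84 days of a 90-day follow-up.

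**2. Two men under the two rules.** Each plans at Week 49 to stay off therapy and restarts shortly after the 60-day visit.

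| | Endpoint text, 4.7, 6.4 | 9.3.2, synopsis methods |
|---|---|---|
| Recovered at the 30-day visit | in, event counted | out, event lost |
| Not recovered by the 60-day visit | in, event-free time usable | out, event-free time lost |

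The two rules define different sets of men.

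**3. Possible size.** Inputs:
- True 12-week recovery on relugolix *p* = 50%. Section 2.2.4.2 reports about half in phase 2.
- True 12-week recovery on leuprolide *p* = 6%. This is an assumption: 6% is the degarelix figure from the same study, and no leuprolide figure is given.
- Restart rate *q* = 20% or 40% over 12 weeks while a man is at risk of restarting. This is also an assumption; the documents give no rate.

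Take constant hazards per 12 weeks, λ = −ln(1 − *p*) and μ = −ln(1 − *q*). Men kept by the literal rule have complete follow-up to day 84, so Kaplan-Meier at that day equals the simple proportion recovered, A/(A + B), where A is kept and recovered and B is kept and not recovered.

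- Restart unrelated to recovery: A/(A + B) = *p*.
- Restart only before recovery: A = λ/(λ + μ) × [1 − (1 − *p*)(1 − *q*)], B = (1 − *p*)(1 − *q*).
- Restart only after recovery: A = λ/(λ − μ) × [(1 − *q*) − (1 − *p*)], B = 1 − *p*.

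Example, before recovery, *q* = 20% (μ = 0.223):
- Relugolix, λ = 0.693: A = 0.693/0.916 × 0.6 = 0.454, B = 0.4, estimate 0.454/0.854 = 53.2%.
- Leuprolide, λ = 0.0619: A = 0.0619/0.285 × 0.248 = 0.054, B = 0.752, estimate 0.054/0.806 = 6.7%.
- Difference 46.5 points, against a true 44.0.

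| Restart pattern | *q* | Relugolix | Leuprolide | Difference | Shift |
|---|---|---|---|---|---|
| Unrelated | 20% or 40% | 50.0% | 6.0% | 44.0 | 0 |
| Only before recovery | 20% | 53.2% | 6.7% | 46.5 | +2.5 |
| Only before recovery | 40% | 57.3% | 7.7% | 49.6 | +5.6 |
| Only after recovery | 20% | 46.9% | 5.4% | 41.5 | −2.5 |
| Only after recovery | 40% | 43.2% | 4.7% | 38.4 | −5.6 |

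A simulation of 2,000,000 men per arm agrees to within 0.1 point; its last row reads 38.5, a shift of −5.5.

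**4. Other comparator values.** At 50% versus 20% (true difference 30.0), the simulated literal rule gives 27.0 to 32.6. At 50% versus 50% with the same restart behaviour, the difference stays at zero while each arm's estimate ranges from 43% to 57%.

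**5. Censoring at restart.** Keeping all men and censoring the unrecovered at restart returns 44.0 in every simulated 50% versus 6% scenario. That is so by construction: restart before recovery was not allowed to depend on how close a man was to recovering.

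**The case against.** The strongest reply is that deletion is inferred. No sentence says that a restarter's data are discarded. The operational sections all select prospectively, so the analysis wording may be loose phrasing for the same men, and the unseen SAP may handle restarts. Part of this stands: intent cannot be read from the text. But the non-start rule appears in both descriptions of the analysis, and an SAP that kept restarters would depart from the protocol's own definition.

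A reader might infer more than the documents support:

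- **That the comparison is certainly distorted, or in a known direction.** Restart before recovery widens the difference, restart after recovery narrows it, and unrelated restart leaves it unchanged.
- **A large error.** If 20 of 100 men restart and true recovery is 50%, the extremes are (50 − 20)/80 = 37.5% and 50/80 = 62.5%. That is a one-arm worst case at an assumed rate and says nothing about the arm difference. Men chosen as able to stay off therapy may restart less often.
- **That relugolix is shown to recover faster than leuprolide.** The 6% belongs to degarelix, and the phase 2 men were treated for 24 weeks, not 48.
- **That the lack of a consecutive-entry rule is part of this fault.** It is a separate matter, and nothing here gives it a size.

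Sampling error is also larger than the shifts shown. With 100 and 50 men, the 95% half-width is 1.96 × √(0.25/100 + 0.0564/50) = 0.118, about 12 points. That limits the practical weight of the point but does not make the rule sound.

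**Conclusion.** The contradiction stands on the text. Two places define the analysis set by later behaviour; the endpoint definitions and the entry rules define it by intention or judgement at the end of treatment. Taken literally, the former conditions on follow-up and can bias both the curves and their difference.

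The size is illustrative: about −5.5 to +5.6 points on a true 44, resting on assumed restart rates of 20% to 40%, constant hazards and a borrowed comparator rate. It is zero if restart is unrelated to recovery, and zero for the difference if the arms share the same recovery and restart pattern. The endpoint is secondary and measured in about 150 men; neither primary evaluation criterion is touched. The correction should be made because it is cheap and removes a selection that the text imposes.

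**What to change.** Reconcile section 9.3.2 and the synopsis statistical methods with the synopsis endpoint list, section 3, section 4.7, section 6.4 and footnote c of Table 1-1:

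1. Define the analysis set at the end of treatment (Week 49) by documented intention not to start alternative therapy, as the endpoint text already does.
2. Keep every man who enters recovery follow-up.
3. Count recoveries observed before restart, and censor men not yet recovered at the start of alternative therapy.
4. Add a sensitivity analysis with restart as a competing event. Censoring may be informative if men restart while testosterone is rising but still below the recovery threshold.

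This concerns only who is analysed and how, not when a man should restart. The cost is wording and one extra analysis. No extra visits are needed, since follow-up before restart is already scheduled and restarters already leave the 60- and 90-day visits.
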